14.5.2 Effect of HeatSticks on the Active Exposure Set

The effects of HeatSticks and other covariates on urinary BoExp is described in the analysis in section 12.6.2.3.. To assess the impact on urinary BoExp with and without adjustment for HeatSticks, the

same model from section 12.6.2.3. will be fitted but without HeatSticks as a covariate. From this model, we will calculate the effect on the endpoints similar to section 12.6.2.3. The estimates will be exponentiated and back-transformed to produce the geometric means and the corresponding 95% confidence intervals. An example of the code is provided below.

```
Proc mixed data=_data_ method=reml;
Class sex;
Model endpoint = baseline sex duration <IAQ covariates> / solution ddfm=kr;
estimate 'Active no HeatSticks' intercept 1 baseline xx sex 0.5 0.5 duration xx
IAQ1 xx ... IAQn xx / alpha=0.05 cl;
Run;
```

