4 REVISION HISTORY

Version	Date of Revision	Description
1.0	05 Feb 2018	
Original version
2.0	19 Apr 2018	
Clarified wording for statistical modelling that estimates will be exponentiated to present the results on the original scale.Updated pseudo code in 11.6.2.1.1. for analysis of carbonyls.Updated pseudo code in 11.6.2.1.2. for analysis of tobacco specific markers.Updated algorithm for active exposure group in section 11.6.2.3, removing the wording 'estimate exposures for each product use group' since there were only Active IQOS users.Updated pseudo code in 11.6.2.3., removing location since it is not part of the model.Added section on post-hoc analysis describing additional analysis to be performed.
3.0	11 Jul 2018	
Added post-hoc analysis to investigate effects of Heatsticks on Urinary BoExp in Compliant Exposure Set.Added post-hoc analysis to estimate effect of no HeatSticks use in the Active Exposure Set.Added post-hoc analysis to estimate pre-event adjusted IAQ parameters during the Events.

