12.6.2.3 Analysis of the Active Exposure Group

To quantify the change between the pre-event and end of study urinary BoExp levels in IQOS Active Users. The change from baseline adjusted for creatine is the dependent variable with baseline, Sex, number of *HeatSticks*, duration of exposure and IAQ parameters (Section 8.2.1) as the covariates. Similar to Section 12.6.1.1, an air quality covariate related to each BoExp is included in the model depending on the endpoint and is described in Appendix 15.2. The same IAQ covariates listed for the

various BoExp is also assessed using a step-down regression approach in the following algorithm. Fit a full model with all covariates

1. Drop one IAQ covariate and re-fit the model.
2. Perform a likelihood ratio test and drop the IAQ covariate with the largest p-value for the likelihood ratio statistic if it is more than 0.05.
3. Repeat steps 2 and 3 until no more IAQ covariates can be dropped.
4. Refit the final model with the IAQ covariates remaining in the model and estimate exposures for the Active IQOS group

An example of the SAS code is shown below,

```
Proc mixed data=_data_ method=reml;
Class sex heatsticks;
Model endpoint = baseline sex heatsticks duration <IAQ covariates> / ddfm=kr;
estimate 'Active' intercept 1 baseline xx sex 0.5 0.5 heatsticks xx duration xx
IAQ1 xx ... IAQn xx / alpha=0.05 cl;
Run;
```

We define xx are the mean of a continuous covariate for participants in the active Exposure Group across all Exposure Events. For air quality covariates, xx is the mean calculated over all Exposure Events.

The LSmeans and corresponding confidence intervals will be exponentiated, back-transformed to the original scale and reported as geometric means with its confidence intervals.

Descriptive statistics and figures of each BoExp for the actively exposed participants will be summarized in the same way as described in Section 12.6.1.2. However, the results will only be stratified by Sex.

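### The post-hoc row labelled 'Active no HeatSticks' estimates the mean change at average use, and comparing it with the adjusted row says little about a HeatStick effect

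*SAP*

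**What the plan says.** The parent analysis is SAP 12.6.2.3. In IQOS Active Users it models change from baseline on baseline, sex, number of HeatSticks, duration and selected air-quality covariates. Its estimate is coded as "estimate 'Active' intercept 1 baseline xx sex 0.5 0.5 heatsticks xx duration xx", followed by the air covariates. The placeholder is explained thus: "We define xx are the mean of a continuous covariate for participants in the active Exposure Group across all Exposure Events". For air covariates it is the mean over all Exposure Events. The same code lists heatsticks in the CLASS statement.

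SAP 14.5.2, under a title announcing the effect of HeatSticks, gives its purpose as "To assess the impact on urinary BoExp with and without adjustment for HeatSticks, the" and continues "same model from section 12.6.2.3. will be fitted but without HeatSticks as a covariate". The model becomes "Model endpoint = baseline sex duration <IAQ covariates> / solution ddfm=kr". Evaluation is unchanged: "From this model, we will calculate the effect on the endpoints similar to section 12.6.2.3". The row is coded "estimate 'Active no HeatSticks' intercept 1 baseline xx sex 0.5 0.5 duration xx", again followed by the air covariates. No HeatStick value appears in it, at zero or otherwise.

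The version 3.0 entry in SAP section 4 describes the addition as "Added post-hoc analysis to estimate effect of no HeatSticks use in the Active Exposure Set".

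**The concern.** A row labelled 'Active no HeatSticks' invites the reader to take it as the biomarker change expected without use. Everyone in the Active Exposure Set (SAP 11.3) attended as an active user, and the row is evaluated at those users' own covariate means. It would report their average change as if it were a no-use level.

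The second difficulty applies even if the label only means that no HeatStick covariate was fitted. If the adjusted and unadjusted estimates agree whatever the dose slope is, their agreement could be taken as reassurance that stick count does not matter, when the comparison has almost no ability to show that it does.

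**Working it through.** The plan states no figure for this analysis, so there is none to reproduce. The argument is algebraic; the simulation only shows its size.

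**Algebra.** Let y be the log change, x the covariates other than HeatSticks, and h the stick count, fitted as continuous. PROC MIXED with no random or repeated term gives least-squares point estimates. With an intercept, the fitted surface passes through the means:

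- with HeatSticks: ȳ = a₁ + b₁·x̄ + g·h̄
- without HeatSticks: ȳ = a₂ + b₂·x̄

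The left-hand side is the same. Evaluated at the means, both models return the sample mean change for any slope g.

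**Departures from exact equality.** Both sections weight sex 0.5/0.5 rather than by the sample proportion p of the reference sex. Each estimate then becomes ȳ + s·(0.5 − p), where s is that model's sex coefficient. By the omitted-variable formula, s without HeatSticks equals s with HeatSticks plus g·d, where d is the sex difference in stick count given the other covariates. The rows therefore differ by g·d·(0.5 − p). A term of the same form arises for each air covariate whose event-level mean differs from its participant-level mean. These terms are small unless sex or air level is tied to stick count and the weights are far from the sample's.

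**Inputs for the illustration.** From the SAP: 20% of 96 seats (Table 1) is 19.2 active users per event, and 4 Exposure Events (12.6.2.1.1) give 76.8, taken as 77. Assumed, because the documents do not give them: mean 6 or 10 sticks with SD 3, slope 0 to 0.10 log units per stick, residual SD 0.4, 70% men, stick count unrelated to sex, one air covariate, and a true no-use ratio of 0.932. There were 2,000 simulated data sets per scenario.

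Results are ratios of last void to baseline:

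| Mean sticks | Slope per stick | 14.5.2 row | 12.6.2.3 at mean sticks | HeatSticks kept, set to 0 |
|---|---|---|---|---|
| 6 | 0 | 0.931 | 0.931 | 0.934 |
| 10 | 0 | 0.931 | 0.931 | 0.936 |
| 6 | 0.02 | 1.051 | 1.051 | 0.934 |
| 10 | 0.02 | 1.137 | 1.137 | 0.936 |
| 6 | 0.05 | 1.261 | 1.261 | 0.934 |
| 10 | 0.05 | 1.535 | 1.536 | 0.936 |
| 6 | 0.10 | 1.707 | 1.708 | 0.934 |
| 10 | 0.10 | 2.532 | 2.533 | 0.936 |

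Hand check of the extremes, using the realised mean counts of 6.07 and 10.01: 0.932 × exp(0.02 × 6.07) = 1.052 and 0.932 × exp(0.10 × 10.01) = 2.536. Both match the 14.5.2 row up to rounding and simulation error.

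With sex weighted by its sample proportion, each model reproduced the raw mean change to about 1e-13. With 0.5/0.5 weights the average ratios agreed within 0.001, and in single data sets the two rows differed by at most 0.081 on the log scale. What moves is precision: the standard error is 0.050 with HeatSticks and 0.050 to 0.063 without. Evaluating at zero sticks has a standard error of 0.11 to 0.17.

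**Contrast within the SAP.** In 14.5.1, the Non-Exposure estimate keeps the cumulative HeatStick term in the model and gives it a coefficient of 0. Section 14.5.2 does not do this.

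**The case against.** The best defence is that 14.5.2 does what its text says. Its stated aim is a comparison with and without adjustment, and in that setting 'no HeatSticks' can mean no HeatSticks covariate. The label sits in example code. The phrase about no use occurs only in the revision history, and a difference between a change log and the current text is not an error. This stands: a reader might infer that the SAP commits to a zero-use estimate and fails to deliver it, but the body makes no such commitment. What remains is an ambiguous label on a row that is not a no-use level.

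A reader might also infer that the two rows must agree exactly. They need not. That result requires HeatSticks to be continuous, whereas the parent code has it in CLASS, so its estimate is not at present a prediction at mean consumption. It also requires the same air covariates in both models. If the stepwise selection is rerun without HeatSticks, the retained set may change, and the simulation included no selection step.

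The comparison is not wholly empty, since dropping HeatSticks can alter the duration and air coefficients and the interval width. But the text promises only the exponentiated estimates and their intervals. The SOLUTION option in the 14.5.2 code would print coefficients from the model that lacks HeatSticks, so it cannot supply the slope.

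Finally, nothing in the documents says that agreement will be presented as absence of a dose effect. That is a foreseeable misreading, not a stated plan.

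**Conclusion.** The concern holds. The 14.5.2 row describes average ad libitum use, not zero use. The with/without comparison is close to uninformative about the HeatStick effect, given a continuous HeatStick term and an unchanged set of air covariates. The near-identity needs no assumption about stick counts or slope beyond the small weighting terms shown above.

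The size of the mislabelling does need such assumptions. It is nil if the slope is zero, and otherwise runs from about 1.05 to 2.53 against about 0.93 over the assumed range. A reader might take one of these fold-changes as the error the study will make; the documents do not support that, because the figures only restate the assumed slope and counts.

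Nor do primary results come into question. This is a post-hoc, supportive analysis in the Active Exposure Set, while the primary models use the Compliant Exposure Set. The point is worth correcting because the fix is cheap and the row is easily misread.

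**What to change.** 1. In 12.6.2.3, remove heatsticks from CLASS, keep it as a continuous covariate, and report its slope with a 95% CI as the HeatStick effect, for example as a ratio per stick. State that the count runs to the end of the event (SAP 8.4) while exposure duration stops at the last void (SAP 5.2), so sticks used after that void are included in the count.
2. In 14.5.2, rename the row 'Active, not adjusted for HeatSticks', and say whether the air covariates are held as selected in 12.6.2.3 or selected again.
3. State that agreement between the two rows is not evidence of no dose effect.
4. Optionally, add a row with heatsticks 0 to the 12.6.2.3 model. Flag it as an extrapolation with a wider interval, with air covariates held at Exposure Event levels, so that it describes a non-user in a room where IQOS is in use.

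The cost is a few code lines and some SAP wording, with no new data. The optional row is less precise: its standard error was about 0.11 to 0.17 on the log scale in the illustration, against 0.05 to 0.06 for the other two rows.

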14.6 Additional Analysis to Account for Pre-Event Levels of IAQ Parameters

The review of the pre-event IAQ data described in section 14.3 suggests that the levels of building background should be taken into account during the statistical analysis of the IAQ parameters. The statistical analysis of IAQ parameters described in sections 12.6.2.1.1, 12.6.2.1.2 and 12.6.2.1.3 will therefore be repeated but the endpoint will be the change from pre-event average instead of the raw values measured during an event. Note that the change from pre-event average will be log-transformed prior to analysis. The estimates from these models will be exponentiated and reported as geometric means for each Event type. Comparisons between Exposure and Non-Exposure Event will be reported as ratio of geometric means. All estimates will be reported together with their corresponding 95% confidence intervals.

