8 DERIVED AND COMPUTED VARIABLES

For each timepoint (baseline urine void and last void), the change from Baseline will be calculated by subtracting the individual subject's Baseline value from the value at the end of the study. Mean change from Baseline is the mean of all individual subjects' change from Baseline values.

The percent change from Baseline will be calculated by subtracting the individual subject's Baseline value from the value at the end of the study and then dividing by the individual's Baseline value and multiplying by 100. Mean percent change from Baseline is the mean of all individual participant' percent change from Baseline values.

When the Baseline value is 0, the percent change from baseline will not be calculated and the number of such cases will be tabulated as "Not Calculated" in the descriptive summaries.

The geometric coefficient of variation (CV) will be calculated using the following formula:

$$CV = 100 \sqrt{e^{\text{var}} - 1}$$

where var = the variance from the log transformed data.

The geometric percent Relative Change (RC) from baseline will be calculated using the following formula:

$$RC = 100 * (\exp(\text{mean}(\ln(x) - \ln(\text{base}))) - 1)$$

where $\ln(x)$ are the natural logarithm of the individual values at the end of the study and $\ln(\text{base})$ are the natural logarithm of the individual baseline values.

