12.6.2.1.4 Descriptive Analysis of Indoor Air Quality parameters

In addition to the statistical analysis of the indoor air quality parameters described in Sections 12.6.2.1.1 to 12.6.2.1.3. The IAQ parameters (formaldehyde, acetaldehyde, acrolein and crotonaldehyde, 3-Ethenylpyridine (3-EP), Nicotine, NNN, NNK, PM1, PM2.5, PM4 and PM10) and will be summarized by time (where applicable), event number and type of event (Exposure vs Non-Exposure). All IAQ values will be log-transformed (base_e) prior to the analysis except the particulate matter values PM1, PM2.5, PM4 and PM10.

All raw IAQ values except particulate matter variables PM1, PM2.5, PM4 and PM10 generated during an event will be listed. For particulate matter parameters only the mean for each sensor during an event will be listed.

Summary statistics (Section 12.1.2) of the IAQ endpoints will also include the percent change between Exposure and Non-Exposure Event, together with 95% CI for IAQ values having at least 50% of the measured values above the limit of quantification (LOQ).

For each IAQ parameter, a plot will be generated by location and exposure type (Exposure vs Non-Exposure) to assess whether differences exist in exposures at different locations.

For carbonyls, exposure vs time will be plotted with separate colors for location and type of Exposure Event. For TSNAs and tobacco specific markers, exposure vs location will be plotted with separate colors for the event type. Lastly, for particles suspended in air, the mean exposure (averaged over the duration of an event) vs location will be plotted with separate colors for each event type.

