**Table 6. Covariates for Analysis of HPHCs in air**

Model	Time Points Used	Endpoint	Covariates
1	Average	Acetaldehyde	Baseline, Event Type, Cumulative Heatstick Consumption at 3 rd Hour
1	Average	Acrolein	Baseline, Event Type, Cumulative Heatstick Consumption at 3 rd Hour
1	Average	Crotonaldehyde	Baseline, Event Type, Cumulative Heatstick Consumption at 3 rd Hour
1	Average	Formaldehyde	Baseline, Event Type, Cumulative Heatstick Consumption at 3 rd Hour
2	All timepoints	Acetaldehyde	Baseline, Event Type, Heatstick Consumption, Alcoholic Beverages Consumption, Heatstick and Alcoholic Beverages interaction
3	Average	Acrolein	Baseline, Event Type, Cumulative Food Consumption during event
3	Average	Crotonaldehyde	Baseline, Event Type, Cumulative Food Consumption during event

Model 1 in Table 6 above describes a basic model relating the average levels of carbonyls to HeatSticks consumption. In this model the dependent variable is the change from baseline of the average reading of the carbonyls. Note that the average reading is taken as the mean of all readings from the three suitcases that were used to collect the carbonyls data. Baseline is the mean reading of all pre-event readings that were taken during a specific event. The endpoint change from baseline will be log-transformed prior to analysis. Baseline, Event type (Exposure or Non-Exposure), cumulative Heatstick usage will be fitted as fixed effects. Estimates of the carbonyl readings at mean levels of the covariates will be calculated for each event type. The estimates will be exponentiated and presented on the original scale. In addition to the estimates at an event level, the relative change in the carbonyls between an Exposure and Non-Exposure Event will be estimated as well. These estimates also be exponentiated and presented as a ratio of geometric means of an Exposure Event relative to a Non-Exposure Event. An example of the SAS code for model 1 is as given below.

```
proc mixed data=data;
class event exposure;
model ch=baseline exposure cumu_heatsticks /ddfm=kr solution;
estimate 'Non-exp 3rd hr' intercept 1 baseline xx exposure 1 0 cumu_heatsticks 0
/e cl alpha=.05;
```

```
estimate 'Exp 3hr hr' intercept 1 baseline yy exposure 0 1 cumu_heatsticks yy/e
cl alpha=.05;
estimate 'Change in carbonyl 3hr hr' intercept 0 baseline xy exposure 1 -1
cumu_heatsticks xy /e cl alpha=.05;
run;
```

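### SAP 14.6 and 14.2 (Models 1 and 3) take the log of a change from the pre-event air level, which is undefined for any change of zero or below, and no handling rule is given

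*SAP*

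**What the plan says.** SAP 14.6 repeats the air analyses of 12.6.2.1.1 (carbonyls), 12.6.2.1.2 (nicotine, 3-ethenylpyridine, nitrosamines) and 12.6.2.1.3 (particulate matter) with a new endpoint: "the endpoint will be the change from pre-event average instead of the raw values measured during an event". It then adds that "the change from pre-event average will be log-transformed prior to analysis". Model estimates are exponentiated to geometric means by event type, and "Comparisons between Exposure and Non-Exposure Event will be reported as ratio of geometric means".

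SAP 14.2 uses the same construction for carbonyls in Model 1: "The endpoint change from baseline will be log-transformed prior to analysis". Model 3 is described as similar to Model 1. The text for Model 2 states no transformation.

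SAP section 8, written for participant data, defines two separate quantities. In the first, "the change from Baseline will be calculated by subtracting" the baseline value from the later value. The second is a log-scale quantity under another name: "The geometric percent Relative Change (RC) from baseline will be calculated using the following formula", the formula being built on ln(x) − ln(base). Neither 14.6 nor 14.2 refers to the second.

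SAP 12.6.2.1.4 log-transforms the air values "except the particulate matter values PM1, PM2.5, PM4 and PM10". The imputation rule in SAP 12.1.4 for values outside the quantification limits is written for urinary biomarkers and creatinine, not for air.

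**The concern.** A difference can be zero or negative, and then it has no logarithm. The rule as written cannot be computed for part of the range of the endpoint, and the SAP offers neither an offset nor a handling rule. Statistical software usually returns a missing value for such a log. The model would then be fitted to increases only, with selection that depends on the outcome and that can differ between event types. Section 14.6 was added so that building background would be taken into account when Exposure and Non-Exposure Events are compared, and that comparison is what would be distorted.

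Two further problems do not depend on any reading being lost. First, the exponentiated contrast of logged differences is a ratio of increments above background, whereas a contrast of log-ratios is a ratio of relative changes, and the SAP does not say which is meant. Second, particulate matter is on the original scale in the planned analysis and on the log scale in its repeat.

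**Working it through.** **Inputs from the SAP.** Four Exposure and two Non-Exposure Events (12.6.2.1.1). Nine carbonyl readings per event, from 3 cases × 3 hours (8.2.2). That gives 4 × 9 = 36 Exposure and 2 × 9 = 18 Non-Exposure readings. The plan states no figure for the share of undefined values, so there is none to reproduce.

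**Assumptions.** The documents give no air data. Readings are taken as independent and lognormal with CV 10% to 50%. The pre-event average is the mean of 9 readings. The true during/pre ratio r runs from 1.0 to 3.0.

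**Share undefined.** With σ² = ln(1 + CV²), treating the mean of 9 pre-event readings as approximately lognormal,

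P(change ≤ 0) ≈ Φ[(m − ln r)/s], where m = σ²/2 − ½ ln(1 + CV²/9) and s² = σ² + ln(1 + CV²/9).

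At CV 20%, m = 0.0196 − 0.0022 = 0.0174 and s = 0.2089.
- r = 1: Φ(0.0174/0.2089) = Φ(0.083) = 0.53.
- r = 1.25: Φ((0.0174 − 0.2231)/0.2089) = Φ(−0.985) = 0.16.

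Simulation of 40,000 events per scenario agrees:

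| CV | no rise | 1.25-fold | 1.5-fold | 2-fold |
|---|---|---|---|---|
| 10% | 52% | 2% | 0% | 0% |
| 20% | 53% | 16% | 3% | 0% |
| 30% | 55% | 28% | 12% | 2% |
| 50% | 58% | 40% | 27% | 12% |

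**Effect on the Exposure/Non-Exposure ratio at CV 20%, if undefined values are dropped.** Retained increments are in units of the pre-event median.

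| True rise, Non-Exposure / Exposure | Lost, Non-Exposure | Lost, Exposure | Ratio from logged differences | Ratio from log-ratios |
|---|---|---|---|---|
| none / none | 53% (9.6 of 18) | 53% (19.2 of 36) | 1.00 | 1.00 |
| none / 1.25-fold | 53% (9.6 of 18) | 16% (5.8 of 36) | 0.232/0.115 = 2.02 | 1.25 |
| 1.5-fold / 1.25-fold | 3% (0.6 of 18) | 16% (5.8 of 36) | 0.54 | 0.83 |
| 2-fold / 3-fold | about 0% | about 0% | 2.10 | 1.50 |

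In the second row the logged-difference ratio depends on the assumed CV: 3.87 at 10%, 2.02 at 20%, 1.61 at 30% and 1.36 at 50%. The log-ratio result is 1.25 at each. In the last row nothing material is lost, yet the answers differ because the quantities differ: (3 − 1)/(2 − 1) = 2 for increments, 3/2 = 1.5 for relative levels.

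**Model 1 of 14.2.** This model averages the event readings too, so loss falls faster as levels rise. With 9 readings on each side and CV 20%, a 1.2-fold rise gives Φ(−ln 1.2/√(2 ln(1 + 0.04/9))) = Φ(−0.182/0.094), about 3%; with no rise it is 50% by symmetry. The model reads as having one value per event, so 4 + 2 = 6 values for four fixed-effect parameters (intercept, baseline, event type, HeatSticks). If both Non-Exposure values were undefined, the event-type contrast could not be estimated.

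**Particulate matter.** 12.6.2.1.3 models the mean reading with no log and no exponentiation, consistent with the exception in 12.6.2.1.4. Section 14.6 names 12.6.2.1.3 among the analyses to be repeated and applies the log to all of them.

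**The case against.** The strongest defence is that the wording is loose and a difference of logs was meant. For urine, SAP 12.6.1 and 15.3 log the biomarkers, model a change from baseline and exponentiate the result, which makes sense only as a change in logged values. Section 14.6 likewise exponentiates and reports ratios. This reading is plausible, but the text does not say it: elsewhere the SAP logs values, here it logs the change, and its own log-scale formula is not cited. Even on that reading the outputs would be event/pre-event ratios, not geometric means of air levels or carbonyl readings on the original scale, and the particulate-matter conflict would remain.

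It can also be said that a ratio of increments above background is a legitimate quantity. That stands where every increment is positive, but the SAP does not ensure this.

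A reader might infer that Non-Exposure Events must lose the most data. The documents do not support that. They contain no air results, both event types serve the same food and drink, and 14.2 examines food and alcohol as possible sources of increases. The direction can vanish or reverse, as the second table shows. Even where the larger share is lost from Non-Exposure Events, more readings can be lost from Exposure Events: with none / 1.25-fold at CV 50%, 10.4 of 18 against 14.5 of 36.

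Nor do the documents show that analytes at the quantification limit would give a change of exactly zero, since no imputation rule for air is stated. That undefined values would be dropped is itself an inference from usual software behaviour.

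**Conclusion.** The point holds as a wrong rule in the text, not as a demonstrated bias in results. Read with the SAP's own definition of change, the endpoint in 14.6 and in 14.2 Models 1 and 3 does not exist for changes of zero or below, and nothing says what happens then. Two analysts could follow the text and report different numbers. The size is conditional: under the stated assumptions, about half or slightly more of the readings are undefined when levels do not rise, and few or none when they double unless the CV is large. The ratio of about 2.0 instead of 1.25 belongs to one scenario (Non-Exposure flat, Exposure up 1.25-fold, CV 20%) and should not be quoted without it. The particulate-matter inconsistency rests on no assumption.

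The reach is limited. These are post-hoc secondary air analyses: the planned air analyses in 12.6.2.1 remain, and the primary urinary analysis does not use them. The wording should be corrected before the background-adjusted ratios are relied on.

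**What to change.** - In 14.6 and in 14.2 Models 1 and 3, define the endpoint as ln(event value) − ln(pre-event average). Every positive reading is then usable. If the increment above background is what is wanted, model the untransformed difference and report a difference, not a ratio of geometric means.
- Label the exponentiated estimates as event/pre-event ratios, and their contrast as the Exposure/Non-Exposure ratio of those ratios.
- State a rule for air values below the quantification limit, covering both pre-event and event readings.
- State the scale of the endpoint for 14.2 Model 2.
- Put particulate matter on one scale in 12.6.2.1.3, 12.6.2.1.4 and 14.6.

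The cost is a few lines of SAP wording, one derivation and a rerun of the affected post-hoc tables. No new data are needed.
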